8.5.2 Benefits

No clear benefits have been identified as efficacy has not been assessed. It is apparent that GBS-NN/NN2 induces an immune response but it is not known if the immune response is protective, as this has not been studied. The immune response generated has been shown to induce IgG1 antibodies; it is the IgG1 antibodies that are actively transported across the placenta. An analysis of the opsonophagocytic activity of the antibodies generated against GBS-NN and GBS-NN/NN2 has shown that the antibodies have functional activity. The antibodies to the GBS-NN vaccine have also demonstrated an ability to completely block the epithelial invasion by GBS, at antibody concentrations below 50 ng/mL. The addition of the N-terminal proteins for Alp1 and Alp2/3 has induced a broader immune response with no additional toxicity^[23].

8.6 Reference Safety Information

Based on the current human exposure to GBS-NN/NN2, there are no expected serious AEs and all suspected unexpected serious adverse reactions will be reported^[233].

8.7 Coronavirus Disease 2019 (COVID-19) Risk/Benefit Assessment

This study is to be conducted in healthy adult participants who are deemed not to be at high risk of COVID-19 as per the latest NHS Guidance

(<https://www.nhs.uk/conditions/coronavirus-covid-19/people-at-higher-risk/whos-at-higher-risk-from-coronavirus/>).

The safety of participants is the primary concern. This study is to be conducted at the Simbec-Orion Clinical Pharmacology Unit which is a Phase I accredited unit with extensive experience in conducting Phase I trials of similar design. Simbec-Orion prioritise the health and wellbeing of their clinical trial participants and, as such, have implemented a number of COVID-19 policies and risk mitigating actions. Prior to attendance at site, participants will be contacted to ensure they are not displaying any COVID-19 symptoms; Site COVID-19 policies will be explained to them at this time. Where appropriate, Perspex screens are in place and appropriate social distancing is enforced. Where this is not possible, appropriate Personal Protective Equipment (PPE) will be worn.

Simbec-Orion Clinical Pharmacology unit is a dedicated trial facility and, as such, staffing levels will not be affected by the potential burden presented by COVID-19 to other medical facilities. All employees present at the clinical site are aware of the COVID-19 specific working requirements and will work to the relevant 'Working Safely' Policy.

Medicines and Healthcare products Regulatory Agency (MHRA) Phase I Accreditation requirement No. 3 details the requirement for an agreement with a local hospital for supporting emergencies arising from the clinical trials performed by Simbec-Orion. This agreement is in place with Cwm Taf University Health Board and Prince Charles Hospital (PCH) for this purpose. Cwm Taf University Health Board and PCH have confirmed capacity to support any acute serious AEs (SAEs) during the COVID-19 pandemic (details contained within the latest current version of the Simbec-Orion Clinical General Risk Assessment).

The Investigational Medicinal Product (IMP) is not an immunosuppressant. There is no scientific evidence that GBS-NN/NN2 vaccine increases a participant's susceptibility to COVID-19 or will exacerbate a participant's condition should they contract COVID-19. In addition, all participants will be under the medical supervision of the Principal Investigator while they are onsite at Simbec.

Both the Study and Site Risk Assessments will be continually monitored and updated throughout the trial and it is currently deemed acceptable to conduct the trial without it impacting or being impacted by the COVID-19 pandemic.

In addition, the sponsor has conducted a risk assessment in consideration of the ongoing COVID-19 vaccine deployment programme including assessment of the potential risks associated with concomitant vaccination whilst participating in this trial.

The sponsor has determined that the outcome of the risk assessment undertaken in conjunction with the study team is that participants will be permitted to have their COVID vaccination whilst in the study and is considered as a concomitant medication with no interaction. Administration of the COVID vaccine and the GBS-NN/NN2 vaccine will be separated by at least 7 days.

Participants will be informed that they are to notify the Simbec-Orion team if they are invited to receive a COVID-19 vaccine at any point during the study so that this may be documented accordingly and the timing of the GBS-NN/NN2 vaccine can be adjusted to allow participants to have their COVID vaccination as it is scheduled.

Concomitant administration of GBS-NN/NN2 during an ongoing round of vaccination will not, to the best extent of available knowledge, compromise the efficacy of any current approved COVID-19 vaccine or otherwise induce or exacerbate any effects of current approved COVID-19 vaccines or have any known undue interactions. The study team will continue to review and monitor any update in terms of COVID-19 vaccine interaction with medications within the relevant therapeutic class for GBS-NN/NN2. This will include an assessment of any further COVID-19 vaccines which receive approval for use during the course of the study.

APPROVED

9 STUDY OBJECTIVES

9.1 Primary Study Objective

- To evaluate the safety over 12 weeks of a single booster dose of the GBS vaccine GBS-NN/NN2, administered 1 to 5 years after completion of the initial primary vaccination course and in comparison to vaccine naïve participants (either placebo recipients from study MVX0002 or new vaccine naïve participants).

9.2 Secondary Study Objectives

- Safety Objectives: To evaluate the long-term safety profile of the GBS-NN/NN2 vaccine 6 months following the booster dose in comparison to vaccine naïve participants (either placebo recipients from study MVX0002 or new vaccine naïve participants) who have received a single first dose of GBS-NN/NN2 vaccine.
- Immunological Objectives:
 - To evaluate the IgG antibody responses, specific to GBS-NN and GBS-NN2 fusion proteins, on Day 1 and Day 85 in previously vaccinated healthy female participants and in comparison to vaccine naïve participants (either placebo recipients from study MVX0002 or new vaccine naïve participants) who have received a single first dose of GBS-NN/NN2 vaccine.
 - To evaluate the IgG antibody responses, specific to AlpCN, RibN, Alp1N and Alp2-3N, on days 1, 8, 29, 57, 85 and 183, in previously vaccinated healthy female participants and in comparison to vaccine naïve participants (either placebo recipients from study MVX0002 or new vaccine naïve participants) who have received a single first dose of GBS-NN/NN2 vaccine.

9.3 Exploratory Study Objectives

- [REDACTED]
- [REDACTED]
- [REDACTED]
- [REDACTED]

10 INVESTIGATIONAL PLAN

10.1 Overall Study Design and Plan

This is an open label vaccine booster follow-up study. Participants who have received a primary course of GBS-NN/NN2 or placebo in Study MVX0002 will be invited to return to receive a booster dose (or first dose in the case of placebo or vaccine naïve participants) 1 to 5 years after the completion of the primary course of vaccination. All participants will receive a single dose of GBS-NN/NN2 containing 50µg of each fusion protein.

A minimum of 30 and a maximum of 40 female participants will be recruited, comprised of between 20 and 30 participants who had received previous vaccination with GBS-NN/NN2 in the MVX0002 study and up to 10 participants who had received placebo in the MVX0002 study. If an insufficient number (<5) of previous placebo recipient participants return to this study, vaccine naïve participants will be recruited.

The study will include 7 visits (Visit 1: Screening Period, Visits 2-6: Treatment Period and Visit 7: Post-study Follow-up).

The clinical phase is anticipated to take place between June/July 2021 and January/February 2022. The conclusion of the study is defined as last participant last visit.

The study will take place in the Clinical Unit of Simbec-Orion Clinical Pharmacology under full medical and nursing supervision.

A schedule of all study assessments is provided in Table 10.7.1.

10.2 General Stopping Criteria

The study will be discontinued if any unacceptable safety findings are identified. This decision will be made jointly by the Principal Investigator (or deputy) and the Sponsor. A written document signed by the Principal Investigator (or deputy) and Sponsor will be produced ratifying the decision.

If any of the following stopping criteria are met, the study will be temporarily halted:

- a ‘serious’ adverse reaction (i.e. a serious adverse event considered at least possibly related to the IMP administration) in one subject.
- ‘severe’ adverse reactions (i.e. severe non-serious adverse events considered as, at least, possibly related to the IMP administration) in two subjects, independent of within or not within the same system-organ-class.

If the study is temporarily halted for any reason including the circumstance where any of the above stopping criteria are fulfilled, the study will only proceed and restart once an appropriate substantial amendment has been submitted and receives regulatory approval from the MHRA and approval from the REC associated with the study. Individual participants may also be withdrawn for any of the reasons outlined in Section 10.5.4.

10.3 Discussion of Study design, including the choice of Control Groups

A large medical need exists for the development of an effective alternative to IAP for the prevention of neonatal GBS infections, as outlined above and a maternal vaccine would be the appropriate solution.

MinervaX has developed a novel GBS vaccine candidate, GBS-NN/NN2, based on the N-termini of the surface proteins of GBS.

The clinical trials with GBS-NN (Study MVX13211) and with GBS-NN/NN2 (Study MVX0002) in healthy non-pregnant women, have shown the potential vaccine to be highly immunogenic well tolerated with a good safety profile.

This study is a follow-on study to assess the safety and immunogenicity of a booster dose of GBS-NN/NN2 vaccine, 1 to 5 years after participants in study MVX0002 have completed the primary vaccination course, in comparison to vaccine naïve participants (either placebo recipients from study MVX0002 or new vaccine naïve participants). The rationale for the inclusion of such participants is as follows:

- To provide a comparison in safety/tolerability and immune response data between individuals who have received a booster dose of the vaccine versus a single dose administration in previously vaccine naïve individuals.
- To add to the growing body of safety and immunogenicity data generated for the GBS-NN/NN2 vaccine following a single dose administration.
- To evaluate the safety/tolerability and immune response following a single dose administration in comparison with the data generated in the MVX0002 study (based on 2 doses of GBS-NN/NN2 vaccine on Day 1 and Day 29).

10.4 Selection of Study Population

All women who have participated in Study MVX0002 with GBS-NN/NN2 will be re-contacted and invited to participate in this study. It is intended to recruit 20 to 30 women who have received a primary course of vaccination with GBS-NN/NN2 and up to 10 women who received placebo in the MVX0002 study. If insufficient (<5) participants who received placebo in Study MVX0002 return to this study, vaccine naïve participants will be recruited.

The following eligibility criteria are designed to select participants for whom protocol treatment and procedures are considered appropriate. All relevant medical and non-medical conditions should be taken into consideration when deciding whether this protocol is suitable for a particular participant.

Deviations from inclusion and exclusion criteria are not allowed as deviations have the potential to impact the scientific integrity of the study, regulatory acceptability or participant safety as such deviations constitute a deliberate breach of Regulation 29 of Statutory Instrument (SI) 2004/1031. Therefore, adherence to the criteria as specified in the protocol is essential.

10.4.1 Inclusion Criteria

To be confirmed at Screening:

1. Women who have participated in study MVX0002, with GBS-NN/NN2 vaccine and received active vaccine or placebo (unless it is necessary to recruit vaccine naïve participants to bolster the number of participants who received placebo in MVX0002).
2. Able to voluntarily provide written informed consent to participate in the study.
3. Healthy female participants aged 18-40 years (vaccine naïve participants only).
4. Female participant of childbearing potential willing to use a highly effective method of contraception (in addition to a condom for male partners), if applicable (unless of non-childbearing potential or where abstaining from sexual intercourse is in line with the preferred and usual lifestyle of the participant) from the first dose until completion of the Day 85 visit. A woman is considered of childbearing potential, i.e. fertile, following menarche and until becoming post-menopausal unless permanently sterile. Permanent sterilisation methods include hysterectomy, bilateral salpingectomy and bilateral oophorectomy. *For the purposes of this study, this definition of a female of childbearing potential applies to all females in the study i.e., those who participated in the MVX0002 study and those who are considered vaccine naïve.*
5. Female participant of non-childbearing potential. *For the purposes of this study, this is defined as the participant being at least 4 months post-surgical sterilisation (including bilateral fallopian tube ligation or bilateral oophorectomy with or without hysterectomy).*
6. Female participant with a negative pregnancy test at Screening and prior to dose.
7. Female participant of menopausal status confirmed by demonstrating at Screening that the serum level of the follicle stimulating hormone (FSH) falls within the respective pathology reference range. In the event a participant's menopausal status has been clearly established (for example, the participant indicates she has been amenorrhoeic for 10 years, confirmed by medical history, etc), but serum FSH levels are not consistent with a postmenopausal status, determination of the participant's eligibility to be included in the study will be at the Investigator's discretion following consultation with the Sponsor.
8. Body mass index (BMI) ≥ 18 and ≤ 30 kg/m² (vaccine naïve participants only).
9. Participants' weight ≥ 50 kg and ≤ 100 kg at Screening (vaccine naïve participants only).
10. Non-smokers for at least 3 months prior to study vaccine administration.
11. No clinically significant abnormal test results for serum biochemistry, haematology and/or urine analyses within 28 days before dose administration of the IMP.
12. Participants with a negative urinary drugs of abuse (DOA) screen (including alcohol) test results, determined within 28 days before dose administration of the IMP (N.B.: A positive test result may be repeated at the Investigator's discretion, if on prescribed opiates resulting in a positive test, participants may be eligible at the investigators discretion).

13. No clinically significant abnormalities in vital signs (supine blood pressure/heart rate, respiration rate, tympanic temperature) determined within 28 days before dose of IMP.
14. Participants with a negative COVID-19 test on admission (Day 1 or Day-1 if deemed appropriate by the Principal Investigator (PI)) if required at the time.

To be re-confirmed prior to dose administration:

1. Participants continue to meet all screening inclusion criteria.
2. Participants with a negative urinary drugs of abuse screen (including alcohol) prior to dose administration.
3. Participants with a negative pregnancy test.
4. Participants with a negative COVID-19 test on admission (Day 1) (or Day -1 if deemed appropriate by the PI) if required at the time.

10.4.2 Exclusion Criteria**To be confirmed at Screening:**

1. Participants who have an autoimmune disease.
2. Participants who have a current infection or any significant illness at Screening (such participants can be rescreened once the active infection or significant illness has resolved).
3. Participants with history or presence of significant cardiovascular disease, pulmonary, hepatic, gallbladder or biliary tract, renal, haematological, gastrointestinal, endocrine, immunologic, dermatological, neurological, psychiatric, autoimmune disease or current infection.
4. Laboratory values at Screening which are deemed by the Investigator to be clinically significantly abnormal.
5. Positive for human immunodeficiency virus (HIV), hepatitis B surface antigen (HBsAg) or hepatitis C virus antibody (HCV Ab).
6. Participation in a clinical drug study during the 90 days or 5 half-lives, whichever is longer, preceding the initial dose in this study (such participants can be rescreened once the 90-day or 5 half-lives period has elapsed).
7. Participants with a history of severe allergic reactions after previous vaccination.
8. Participants with a history of hypersensitivity to the IMP or any of the excipients within the IMP or documented allergy to aminoglycosides.
9. Participants who have received any vaccine within 7 days of dosing, or who are planning to receive a vaccine up to 7 days after receiving the GBS-NN/NN2 vaccine.
10. Participants who have received immunosuppressive therapy within the 6 months prior to Screening.
11. Participants with tattoos at the proposed site of vaccine administration.
12. Participants who, in the opinion of the Investigator, are unsuitable for participation in the study.

13. Pregnant or breast feeding.
14. Current or history of drug or alcohol abuse, or a positive urine alcohol test prior to dosing (prescribed opiates are acceptable).
15. Use of prescription or non-prescription drugs, including vitamins, herbal and dietary supplements within 28 days or 5 half-lives (whichever is longer) prior to the first dose of IMP with the exception of contraceptives and paracetamol (*applies to vaccine naïve participants i.e., those who did not participate in the MVX0002 study and participants from the MVX0002 study (both active and placebo) who have not developed new medical conditions which require the use of chronic medications considered as permitted*). If participants who participated in the MVX0002 study (either active or placebo recipients) have developed new medical conditions which require the use of chronic medications that do not affect the immune system, the inclusion of such participants will be permitted at the discretion of the Investigator on a case-by-case basis and, only if it is considered that the inclusion within the MVX0003 study will not be detrimental to participant safety.
16. Donation of blood or blood products within 90 days prior to vaccine administration.

To be re-confirmed prior to dose administration:

1. Development of any exclusion criteria since the Screening visit.
2. Use of prescription or non-prescription drugs, including vitamins, herbal and dietary supplements since the Screening visit with the exception of contraceptives and paracetamol (*applies to vaccine naïve participants i.e., those who did not participate in the MVX0002 study and participants from the MVX0002 study (both active and placebo) who have not developed new medical conditions which require the use of chronic medications considered as permitted*).
3. Participation in a clinical study since the Screening visit.
4. Donation of blood or blood products since the Screening visit.

10.5 Additional Advice and Restrictions for Study Population

10.5.1 Contraception

Females of childbearing potential must have had a negative serum pregnancy test at Screening and a negative urine pregnancy test prior to dose.

To prevent pregnancy, female participants of childbearing potential must be willing to use a highly effective method of contraception (in addition to a condom for male partners), if applicable (unless of non-childbearing potential or where abstaining from sexual intercourse was in-line with the preferred and usual lifestyle of the participant [periodic abstinence (e.g., calendar, ovulation, symptothermal, post-ovulation methods) and withdrawal are not acceptable methods of contraception]) from the first dose until completion of the Day 85 visit.

Highly effective methods of contraception include:

- Combined (oestrogen and progestogen containing) hormonal contraception (oral, intravaginal and transdermal) associated with inhibition of ovulation,

- Progestogen-only hormonal contraception (oral, injectable and implantable) associated with inhibition of ovulation,
- Intrauterine device (IUD),
- Intrauterine hormone-releasing system (IUS),
- Bilateral tubal occlusion,
- Vasectomised partner (with the appropriate post-vasectomy documentation of the absence of sperm in the ejaculate). In the absence of such documentation, condoms will be required for the male partners. For female participants on the study, the vasectomised male partner should be the sole partner for that participant.

The chosen contraception method(s) must have been followed from the first dose until at least Day 85 of the study.

Participants do not have to use highly effective contraception following the Day 85 visit. Should any participant become pregnant between Day 86 and Day 183, permission will be sought to follow the pregnancy and to obtain data on the outcome of the pregnancy.

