| This is an open label vaccine booster follow-up study. Participants who had received a primary course of GBS-NN/NN2 or placebo in Study MVX0002 will be invited to return to receive a booster dose (or first dose in the case of placebo or vaccine naïve participants) 1 to 5 years after the completion of the primary course of vaccination. All participants will receive a single dose of GBS-NN/NN2 containing 50µg of each fusion protein. |

A minimum of 30 and a maximum of 40 female participants will be recruited, comprised of between 20 and 30 participants who had received previous vaccination with GBS-NN/NN2 in the MVX0002 study and up to 10 participants who had received placebo in the MVX0002 study. If an insufficient number of previous placebo recipient participants return to this study, vaccine naïve participants will be recruited.

The study will include 7 visits (Visit 1: Screening Period, Visits 2-6: Treatment Period and Visit 7: Post-study Follow-up).

Visit 1 - Screening Period (Day -28 to Day -1):

After signing the informed consent form, Screening assessments will be performed within 28 days of the planned dose to ensure the eligibility of participants. Screening assessments will include:

- Inclusion/Exclusion Criteria
- Demographic data
- Subject number and Investigational Medicinal Product received in MVX0002 study
- Medical history
- Physical examination (full)
- Height, weight and body mass index (BMI)
- Vital signs (supine heart rate, blood pressure, tympanic temperature and respiration rate)
- 12-lead ECG
- Virology (human immunodeficiency virus (HIV), hepatitis B surface antigen (HBsAg) and hepatitis C virus antibody (HCV Ab))
- Laboratory safety tests (biochemistry, haematology)
- Urinalysis
- Urine drugs of abuse including alcohol and cotinine
- Serum pregnancy test
- Follicle Stimulating Hormone Test (Postmenopausal women only)
- Prior and concomitant medication

Visits 2-6 - Treatment Period (Day 1 to Day 85):

Visit 2 (Day 1):

Participants will be admitted to the clinic in the morning of Day 1 and will remain in the unit until the 30 minutes (min) post-dose scheduled assessments. The following procedures will be performed on Day 1.

- COVID-19 Reverse Transcription Polymerase Chain Reaction Test: Pre-dose (can be performed at Visit 1, Day -1 at the discretion of the Principal Investigator (PI))
- Physical examination: Pre-dose (brief) and 30 min (\pm 5 min) post-dose (Symptom-Directed Physical Examination prior to discharge)

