10.5.4 Removal of Participants from Further Assessment

Each participant will be informed of their right to withdraw from the study at any time and for any reason.

An Investigator may withdraw participants from the study at any time for any of the following reasons:

- If a participant experiences a serious or intolerable AE, that prevents them from continuing. Participants will be followed-up for safety and until resolution of the AE unless lost to follow-up.
- If a participant incurs a significant protocol violation which impacts on their safety or the scientific integrity of the study.
- At the request of the Sponsor.
- If it is considered that the participant's health is compromised by remaining in the study or the participant is not sufficiently cooperative.
- If a participant is lost to follow-up.
- Pregnancy before Day 85 (will be discussed with the participant and sponsor to establish continuation of monitoring required).

All cases will be discussed on a case-by-case basis with the sponsor. The decision and the reason for any participant withdrawal will be recorded on the study completion form of the electronic case report form (eCRF).

If a participant is withdrawn or chooses to withdraw from the study for any reason every possible effort will be made to perform the evaluations described for the post-study follow-up (see Table 10.7.1). The data collected from withdrawn participants will be included in the study report.

In the event of any abnormalities considered to be clinically significant, participants will be followed-up with appropriate medical management until values are considered to be clinically acceptable. Referral or collaborative care will be organised if considered necessary.

A minimum of 30 and maximum of 40 female participants are required to complete the study. Participants who withdraw from the study before receiving any IMP will be replaced if suitable reserves are available. Participants who are withdrawn from the study due to significant drug-related AEs will not be replaced. Replacement of all other participants withdrawn from the study after receiving IMP will be decided on a case-by-case basis by the Principal Investigator (or deputy) and Sponsor.

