10.7 Efficacy and Safety Variables

10.7.1 Efficacy and Safety Measurements Assessed and Flow Chart

A schedule of study assessments is provided in the Study Flow Chart, Table 10.7.1.

Simbec-Orion personnel who have been appropriately trained will carry out study procedures.

Where more than 1 procedure is scheduled for the same time-point, the following order of priority will apply:

1. PD blood sampling: Post-vaccination blood samples collected outside of the defined deviation windows will be recorded as protocol deviations: ± 1 day on Day 8, ± 2 days on Day 29 and Day 57, ± 5 days on Day 85 and ± 7 days on Day 183.
2. Vital signs: Vital sign assessments performed outside of the defined deviation windows will be recorded as protocol deviations: ± 5 minute (min) on Day 1, ± 1 day on Day 8, ± 2 days on Day 29 and Day 57, ± 5 days on Day 85 and ± 7 days on Day 183.

Baseline PD samples and vital sign assessments will be performed within the 1 h before dosing.

Table 10.7.1 Study Flow Chart

| | Screening Period | Treatment Period | | | | | | Safety Follow-Up |
|--|-------------------|------------------|------------------|--------------------|--------------------|--------------------|---------------------|------------------|
| | | Visit 1 | Visit 2 | Visit 3 | Visit 4 | | | |
| Assessment | Day -28 to Day -1 | Day 1 | Day 8 (±1day) | Day 29 (±2days) | Day 57 (±2days) | Day 85 (±5days) | Day 183 (±7days) | |
| Informed Consent | X | | | | | | | |
| Inclusion/Exclusion Criteria | X | | | | | | | |
| Subject number and IMP received in MXV0002 study | X | | | | | | | |
| Demography | X | | | | | | | |
| Medical History | X | | | | | | | |
| Physical Examination ¹ | X (Full) | X (Brief & SDPE) | X (Brief) | X (Brief) | | | | X (Brief) |
| Height, Weight, BMI | X | | | | | | | |
| Vital Signs ² | X | X | X | X | X | X | X | |
| 12-lead ECG | X | | | | | | | |
| Urinalysis | X | | | | | | | X |
| Laboratory Safety Tests (Biochemistry and Haematology) | X | | X | X | X | | | X |
| Virology (HIV, HBsAg and HCV Ab) | X | | | | | | | |
| Pregnancy Test | X (Serum) | X (Urine) | | | | | | X (Urine) |
| FSH ³ | X | | | | | | | |
| Urine DOA including alcohol and cotinine tests | X | X | | | | | | |
| Review of Participant Eligibility | | X | | | | | | |
| Administration Investigational vaccine | | X | | | | | | |
| PD Blood Sample – Antibody Response ⁴ | | X | X | X | X | X | X | X |
| Exploratory Blood Sample – [REDACTED] ⁵ | | X | X | | | | | |

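### Contraception is required only from the single Day 1 dose, so a conception in the days before dosing, possibly too recent for the Day 1 urine test, is not guarded against

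*Protocol*

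**What the plan says.** Section 10.5.1 (Contraception) fixes the period: "The chosen contraception method(s) must have been followed from the first dose until at least Day 85 of the study". Inclusion criterion 4 in section 10.4.1 gives the same limits, "from the first dose until completion of the Day 85 visit", and the synopsis repeats that criterion. No section requires contraception or abstinence between Screening and dosing.

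That interval can be long. According to the synopsis, "Screening assessments will be performed within 28 days of the planned dose to ensure the eligibility of participants", and Table 10.7.1 shows Screening as Day -28 to Day -1.

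Pregnancy is excluded by criterion 13 of section 10.4.2, "Pregnant or breast feeding". The list to be re-confirmed before dosing includes "Development of any exclusion criteria since the Screening visit". Two tests support this: "Females of childbearing potential must have had a negative serum pregnancy test at Screening and a negative urine pregnancy test prior to dose".

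After Day 1, the synopsis visit lists and Table 10.7.1 show no pregnancy test at Days 8, 29, 57 or 85. The next one is a urine test at Day 183 (±7).

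**The concern.** Every participant receives one injection, on Day 1. The pregnancies exposed at the moment of injection are those conceived before Day 1. The contraception rule begins at that moment and runs for the 84 days after it. For the days that decide whether a pregnant woman is dosed, the plan relies on testing alone, and a test cannot show a very recent conception. The Screening serum test does not help here, because a conception after Screening comes later than that sample.

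Other commitments in the same protocol do reach back before dosing: 28 days or longer without most medicines (10.4.2, criterion 15), 90 days without blood donation (10.4.2, criterion 16) and three months without smoking (10.4.1, criterion 10). Contraception does not.

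At stake is the chance of dosing a woman whose pregnancy is too early to detect, in a study that means to exclude pregnant women.

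**Working it through.** The plan states no figure on this point, so there is none to reproduce. The check is day arithmetic on the schedule plus one assumed quantity.

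**Inputs**
- Screening to dosing, *k*: 1 to 28 days (Day -1 to Day -28; synopsis and Table 10.7.1).
- Contraception required before dosing: 0 days (synopsis, 10.4.1 criterion 4, 10.5.1).
- Lag from conception to a positive test, *d*: 14 days, range 10-21. This is an assumption; the documents give no value.
- Day 29 visit window: ±2 days (Table 10.7.1).

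**Step 1. Window that the Day 1 test cannot see.** A conception fewer than *d* days before dosing does not yet show. The window is the last 14 (10-21) days before Day 1. Even at 21 days it fits inside a 28-day Screening period, so the gap exists at every value in the range.

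**Step 2. Share of that window covered if contraception started at Screening.** Share = min(*k*, *d*) / *d*.

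| Screening before dosing (*k*) | *d* = 14 | Range for *d* = 10-21 |
|---|---|---|
| 1 day | 1/14 = 7% | 1/21 = 5% to 1/10 = 10% |
| 7 days | 7/14 = 50% | 7/21 = 33% to 7/10 = 70% |
| 14 days | 100% | 14/21 = 67% to 100% |
| 21 days or more | 100% | 100% |

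The earlier start closes the window when Screening is early and does little when Screening falls just before dosing.

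**Step 3. What a Day 29 assay would add.** The visit falls 28 ± 2 = 26 to 30 days after dosing. The shortest interval, 26 days, exceeds the longest assumed lag, 21 days. Every pregnancy conceived before dosing and still continuing would therefore show. The latest conception it could show is Day 29 - 14 = Day 15, with a range of Day 27 - 21 = Day 6 to Day 31 - 10 = Day 21. This is detection and dating after the dose; it prevents nothing.

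**Step 4. Scale.** Among women already using a method, with an assumed failure rate of 1-5% a year (not in the documents), conceptions expected in the last 14 pre-dose days are:
- 30 × 0.01 × 14/365.25 = 0.01
- 40 × 0.05 × 14/365.25 = 0.08

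This is the background that remains after the change as well. The avoidable part comes from women who would use no method until dosing. The documents do not say how many there would be, so I put no number on it.

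**The case against.** The strongest reply is that the protocol already applies its exclusion with two tests, the second mandatory before the injection, and that a contraceptive lead-in is a design preference. The amendment log also shows that section 10.5.1 was revised at the regulator's request. The practical gap is narrow too. Criterion 4 is checked at Screening, and most of the listed methods (intrauterine devices, tubal occlusion, a vasectomised partner, hormonal methods that inhibit ovulation) would have to be in place already to count from the moment of dosing. Sterilised, postmenopausal and abstinent women are also eligible.

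Most of this stands as a limit on size. It does not close the gap: neither pre-dose test can see a conception in the last days, and the log entry concerns highly effective methods, not the start date.

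Three stronger readings are tempting, and the documents do not support them.
- *The protocol contradicts itself.* It does not. It excludes pregnancy, tests for it twice and re-confirms before dosing. The start date is poorly placed, not inconsistent.
- *A pregnancy in the 12 weeks after dosing would stay unknown until Day 183 and go unfollowed.* The gap between scheduled tests is 182 ± 7 = 175-189 days, but there are clinic visits with adverse-event checks at Days 8, 29, 57 and 85. Footnote 2 to Table 10.7.2 allows for discretionary tests. Section 10.7.1.4.1 requires a report within 24 hours of first knowledge and calls for follow-up to outcome, with no Day 85 cut-off.
- *Repeated tests up to Day 85 are needed, and would spare future-work blood.* Later tests cannot undo a single exposure. No section stops that sampling on pregnancy, and withdrawal is discretionary: "An Investigator may withdraw participants from the study at any time for any of the following reasons".

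**Conclusion.** The point holds as a cheap improvement that the sponsor could make. The contraception requirement starts at the dose, whereas exposure at the injection depends on the days before it. The uncovered window is about the last 14 days before dosing (10-21 under the assumed lag), within a Screening period of up to 28 days.

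The consequence is small. That few women would begin a method only at dosing is a judgement from the listed methods, not a count in the documents. Section 8.3 reports no adverse embryo-foetal effect in rats or rabbits. Section 8.5.1 reports 48 pregnant women given a first dose, with the vaccine well tolerated, and the product is intended for use in pregnancy. The conclusion that a gap exists does not depend on the exact lag; the share that the change would close depends on both the lag and the date of Screening.

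**What to change.** In the synopsis (main inclusion criterion 4), section 10.4.1 (criterion 4) and section 10.5.1, start the contraception requirement at Screening instead of the first dose. All three places must change together, or the protocol will disagree with itself. The cost is up to 28 more days of contraception commitment per woman, with no extra visit or sample. The limit is a late Screening: at Day -1 the change covers only 5-10% of the window.

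Optional addition: run a pregnancy assay on the biochemistry serum already drawn at Day 29 (±2), as footnote 1 to Table 10.7.2 does at Screening. Amend Table 10.7.1, section 10.7.1.1.6 and the synopsis visit list to match. This is one assay per woman (30-40 in all) with no further blood. It would identify a continuing pregnancy conceived before dosing, including after a late Screening, and help to date it, but it would not prevent exposure.
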